### **6.6.3 Corneal Ulceration**

Following an ocular event, the results of eye investigation must be recorded in the CRF by the investigator. Patients experiencing corneal ulceration will not be permitted to restart AZD9291 treatment.

### **6.6.4 Skin reactions**

Recommendations for appropriate management of skin reactions, including guidance on dose-adjustments for clinically significant and/or intolerable skin reactions that are considered by the investigator to be causally related to AZD9291 will be provided to clinicians.

### **6.6.5 Diarrhoea**

Recommendations for appropriate management of diarrhoea, including uncomplicated CTCAE grade  $\leq 2$ , and dose-adjustments for AEs of diarrhoea that are of CTCAE grade  $\geq 3$  or that are clinically significant and/or intolerable and considered by the investigator to be causally related to AZD9291, will be provided to participants in the study.

For further guidance on skin reactions and diarrhoea, please refer to “Guidance for the Management of Adverse Events in Studies using 80 mg AZD9291”

## **6.7 Study governance and oversight**

An Executive Steering Committee will be set up. It will involve 7 experts with the relevant knowledge and experience required for the study. This Executive Committee will have the executive oversight and supervision of the study. It will also be involved in the publication strategy of the study.

## **7. DATA MANAGEMENT**

### **7.1 Collection, monitoring, processing of data and archiving**

Data management will be performed by PAREXEL staff according to the Data Management Plan.

Data collected will include descriptive patient demographics, information needed to determine patient eligibility (including medical history, past and current disease characteristics, and tumor EGFR mutational status), AZD9291 exposure (including starting dose, dose adjustments or discontinuations), investigator-reported efficacy (including tumor response and disease progression), OS, and safety (including serious adverse events, adverse events leading dose-modification, and adverse event of special interest [interstitial lung disease/pneumonitis-like events, and QTc prolongation events]).

Data will be entered in the web-based data capture (WBDC) system at the Investigator's site. The Investigator (or delegate) will be responsible for entering data into the WBDC system and according to the Investigator Instructions Manual. The Investigator Instructions Manual will also provide the study site with data entry instructions.

Data entered in the WBDC system will be immediately saved to a central database and changes tracked to provide an audit trail. When data have been entered, reviewed and edited, the Investigator will be notified to sign the CRF electronically as per the agreed project process. A copy of the CRF will be archived at the Investigator's site.

### **7.2 Reporting and publication of data**

AstraZeneca will prepare a Study Report within 12 months after database lock or completion of the study. AstraZeneca is obliged to analyse and report all study data as described in the protocol.

In accordance with the Declaration of Helsinki, both authors and publishers have ethical obligations. In publication of the results of this study, the authors are obliged to preserve the accuracy of the results. AstraZeneca endeavours to publish the results of this study and is committed to ensure that the data are reported in a responsible and coherent manner.

AstraZeneca seeks to ensure that publications in biomedical journals follow the guidelines established by the International Committee of Medical Journal Editors (ICMJE) and published in its *Uniform Requirements of Manuscripts Submitted to Biomedical Journals*.

AstraZeneca is committed to ensuring that authorship for all publications must comply with the criteria defined by the ICMJE. These state that: "*Each author must have participated sufficiently in the work to take public responsibility for the content.*"

AstraZeneca believes that participation solely in the collection of data or drafting the manuscript does not justify authorship. These conditions apply equally to external investigators and to AstraZeneca employees.

Other members of the group should be listed in the acknowledgments as appropriate.

Publication or presentation of data subsets from individual institutions, regions or countries participating in this global multicentre study may precede the primary manuscript with the approval of the AZ global study team. The AZ global study team will determine if in certain instances publication of institution, regional or country-specific data by the participating country may precede the primary global publication.

## 8. INVESTIGATIONAL PRODUCT

### 8.1 Identity and dose of investigational product – AZD9291

AZD9291 will be supplied as tablets for oral administration as a single daily dose of 80 mg. Each bottle will contain sufficient AZD9291 treatment for 21 days, plus overage. 40 mg tablets will be supplied as needed upon request to the AstraZeneca representative.

Investigational product	Dosage form and strength
AZD9291	40 mg Tablets 80 mg Tablets

The tablets can be taken with or without food and should be swallowed whole with water. The tablet should not be crushed, split or chewed.

If the patient is unable to swallow the tablet, it may first be dispersed in 50 mL of non-carbonated water. The tablet should be dropped in the water, without crushing, stirred until dispersed and immediately swallowed. An additional half a glass of water should be added to ensure that no residue remains and then immediately swallowed.

If administration via nasogastric tube is required, the same process as above should be followed but using volumes of 15 mL for the initial dispersion and 10 mL for the residue rinses. The total liquid should be administered as per the nasogastric tube instructions with appropriate water flushes

The initial dose of AZD9291 80 mg daily can be reduced to 40 mg once daily under circumstances described in Section 6.6.

Doses should be taken approximately 24 hours apart at the same time point each day. Doses should not be missed. If a patient misses taking a scheduled dose, within a window of 12 hours, it is acceptable to take the dose. If it is more than 12 hours after the scheduled dose time, the missed dose must not be taken, and patients must be instructed to take the next dose at the next scheduled time. If a patient vomits after taking their AZD9291 treatment, they must not make up for this dose, but must take the next scheduled dose.

Any change from dosing schedule, dose interruptions, or dose reductions must be recorded in the CRF.

Tablets will be packed in high-density polyethylene bottles with child-resistant closures. Bottles will be dispensed to patients in the packaging provided. The packaging includes bottles, caps and a label. Bottle tamper must not be broken prior to dispensing AZD9291 to a patient.

Additional information about AZD9291 may be found in the IB.

## **8.2 Labeling**

Labels for AZD9291 will be prepared in accordance with Good Manufacturing Practice (GMP) and local regulatory guidelines. Label text will be translated into local language.

The label will include the Name of the Sponsor, Protocol Code, For Clinical Trial use only, and/or any other market specific requirements.

Patient's leaflet will be inserted if required per local regulations

## **8.3 Storage**

All IP must be kept in a secure place under appropriate storage conditions. The IP label on the bottles specifies the appropriate storage.

## **8.4 Compliance**

The administration of AZD9291 must be documented in the appropriate sections of the CRF. Patients must return all unused IP and empty containers to the investigator.

## **8.5 Accountability**

The IP provided for this study will be used only as directed in the study protocol. The study personnel will account for all IP dispensed to and returned from the patient.

The study personnel at the investigational site will account for all treatments dispensed and for appropriate return or destruction. The site is required to maintain documentation of the delivery, return and destruction of IP. AstraZeneca representatives will review and collect this documentation.

# **9. STATISTICAL ANALYSES**

Statistical analysis and generation of all tables, listings and figures will be performed by using SAS® (SAS Institute, North Carolina), version 9.2 or higher.

The analyses of the data collected within this study will be descriptive only.

## **9.1 Statistical evaluation-general aspects**

A Statistical Analysis Plan (SAP) will be prepared and finalised prior to first subject in (FSI). The aim of the study is to assess efficacy and safety of AZD9291 in a real world setting.

## **9.2 Description of outcome variables in relation to objectives and hypotheses**

Analysis will be conducted to evaluate the following as available in the CRF:

- Baseline characteristics: demographics, relevant medical history, disease characteristics, cancer treatment history.
- Exposure to AZD9291
- Response Rate (RR):  
RR is defined as the percentage of patients with a best response of ‘responding’ by investigator assessment as recorded in the CRF.
- Overall Survival (OS):  
Overall survival is defined as the time from the date of first dose of AZD9291 in this study until death due to any cause. Any subject not known to have died at the time of analysis will be censored based on the last recorded date on which the subject was known to be alive.
- Progression Free Survival (PFS)  
PFS is defined as the time from first dose of AZD9291 in this study until the date of disease progression as recorded in CRF or death (by any cause in the absence of progression) regardless of whether the subject withdraws from therapy or receives another anti-cancer therapy prior to progression. Subjects who have not progressed or died at the time of analysis will be censored at the time of the latest date of assessment.
- Time to treatment discontinuation (TTD):  
TTD is defined as the time from the date of first dose of AZD9291 in this study until the date of AZD9291 discontinuation for any reason including disease progression, treatment toxicity, death or other reason as recorded in CRF. Subjects who are still on treatment at the time of analysis will be censored at the date of last dose received.
- Adverse events  
Serious Adverse Events [SAEs], adverse events leading to dose modification, and adverse events of special interest

## **9.3 Description of analysis sets**

Full analysis set (FAS)

The full analysis set will include all subjects who received at least one dose of study treatment.

## **9.4 Methods for statistical analyses**

All analyses will be performed on the FAS population. No statistical tests will be performed, the statistical analyses will be descriptive.

Efficacy analyses will be repeated by cohorts defined by number and type of previous treatment lines and by other pre-defined subgroups of interest as pre-specified in the SAP.

Data will be summarized using descriptive statistics as appropriate. Continuous variables will be summarised by the number of observations (n), mean, standard deviation (SD), median, quartiles (Q1 and Q3), minimum, and maximum. Categorical variables will be summarised by frequency counts and percentages for each category.

#### **9.4.1 Evaluation of primary efficacy objective**

OS will be summarized using Kaplan-Meier (KM) estimates of the median time to death or censoring and quartiles together with their 95% confidence intervals (CIs). KM estimates of the OS rate at appropriate time points (to be defined in SAP) will be presented as well. A plot of the KM overall survival curve will be produced.

#### **9.4.2 Evaluation of secondary efficacy objectives**

PFS and TTD will be summarized similarly to OS using KM estimates of the median times to progression or death or treatment discontinuation, and quartiles together with their 95% CIs. KM estimates of the PFS or TTD rate at appropriate time points (to be defined in SAP) will be presented as well. A plot of the KM PFS and TTD curve will be produced.

The response rate will be summarised together with the 95% CI.

#### **9.4.3 Safety analysis**

Safety and tolerability will be assessed in terms of AEs. These will be collected for all subjects.

- Adverse events  
SAEs and adverse events leading to study drug discontinuation will be summarised by MedDRA preferred terms and CTCAE grade.

Any AE occurring within 30 days of discontinuation of investigational product (ie, the last dose of AZD9291) or until disease progression, whichever is the latest, will be included in the AE summaries.

- Adverse events of special interest  
Adverse events of special interest (for example interstitial lung disease/pneumonitis-like events; QTc prolongation events) will be summarised by pre-defined categories described in the SAP.

#### **9.4.4 Interim analysis**

Interim analysis of the global data will take place annually for the first three years (i.e. at approximately 12, 24 and 36 months from the start of recruitment) to provide annual updates of key study measures as specified in the SAP. Regional and country level analysis may also be performed at these time points if deemed appropriate.

The final analysis will take place approximately 5 years after the start of recruitment, depending on the date of actual global study closure.

## 9.5 Determination of sample size

OS is the primary efficacy endpoint of interest for this study. Median OS is assumed to be approximately 21-25 months in patients with Advanced/Metastatic Epidermal Growth Factor Receptor (EGFR) T790M Mutation-Positive Non-Small Cell Lung Cancer (NSCLC) who have received prior therapy with an EGFR Tyrosine Kinase Inhibitor (EGFR-TKI) receiving AZD9291. While the sample size is not known a priori illustrations of the precision with which OS could be calculated from this real world study are given in the table below. These illustrations assume a study length of 58 months with non-uniform accrual over 40 months and that OS is exponentially distributed.

N	21		23		25	
	n events	95% CI median OS*	n events	95% CI median OS*	n events	95% CI median OS*
500	313	18.8-23.5	297	20.5-25.8	283	22.3-28.1
1000	627	19.4-22.7	595	21.2-24.9	566	23.0-27.1
1500	941	19.7-22.4	893	21.5-24.6	800	23.3-26.8
2000	1255	19.9-22.2	1191	21.7-24.3	1133	23.6-26.5
3000	1883	20.1-22.0	1787	22.0-24.1	1700	23.8-26.2
3500	2197	20.1-21.9	2085	22.0-24.0	1983	23.9-26.1

\*based on the formula in [Collett 1994](#)

Therefore if 3500 patients enter the study globally and the median OS is 25 months the 95% CI around this survival figure would be approximately 23.9-26.1 months. For Europe, assuming recruitment of 1000 patients the equivalent 95% CI would be approximately 23.0-27.1 months.

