#### **Study site(s) and number of patients planned**

Approximately 600 patients will be enrolled (dosed) in Europe. The recruitment will be increased beyond that as the study will expand in other regions of the world (America, Asia). Total recruitment for all regions (including China) is expected to be approximately 3500 patients, depending on recruitment speed and national reimbursement timelines

---

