### **Statistical methods**

As the objective of the study is to collect physician-reported real world efficacy and safety data while offering access to AZD9291 to patients with significant unmet medical need, a total pre-defined recruitment target of treated patients is not applicable for this study.

All data will be presented for the overall full analysis set, and also by cohorts defined by number and type of previous treatment lines for the advanced disease. Descriptive statistics will be used for all variables, as appropriate. Continuous variables will be summarised by the number of observations, mean, standard deviation, median, minimum, and maximum. Categorical variables will be summarised by frequency counts and percentages for each category. OS, time to treatment discontinuation (TTD) and progression-free survival (PFS) will be summarized using Kaplan-Meier estimates of the median event time and quartiles together with their 95% confidence intervals.

TABLE OF CONTENTS	PAGE
PROTOCOL SYNOPSIS .....	2
TABLE OF CONTENTS .....	5
LIST OF ABBREVIATIONS AND DEFINITION OF TERMS.....	8
1. INTRODUCTION .....	10
1.1 Current non-small cell lung cancer (NSCLC)-related treatment patterns .....	10
1.2 Background and rationale for AZD9291 .....	11
1.3 Rationale for dose selection .....	11
1.4 Benefit/risk and ethical assessment.....	12
1.4.1 Nonclinical data .....	12
1.4.2 Clinical data .....	12
1.4.2.1 Study D5160C00005.....	13
1.4.2.2 Study D5160C00001 .....	14
1.4.2.3 Study D5160C00002.....	15
1.4.2.4 Study D5160C00003.....	15
1.4.3 Conclusions.....	15
2. STUDY OBJECTIVE .....	17
3. PATIENT SELECTION .....	17
3.1 Inclusion criteria .....	17
3.2 Exclusion criteria .....	18
4. STUDY CONDUCT .....	19
4.1 Study Plan .....	19
4.2 Restrictions .....	23
4.3 Discontinuation from study treatment .....	24
4.3.1 Procedures for discontinuation of a subject from study treatment.....	25
4.4 Patient Withdrawal or Study Termination .....	25
5. STUDY MEASURES .....	26
6. SAFETY REPORTING AND MEDICAL MANAGEMENT .....	28
6.1 Definition of adverse events .....	28
6.2 Definition of serious adverse events .....	28
6.2.1 Handling of deaths .....	29
6.2.2 Hy's Law.....	30

6.3	Reporting of serious adverse events.....	30
6.4	Overdose .....	30
6.5	Pregnancy.....	31
6.5.1	Maternal exposure.....	31
6.5.2	Paternal exposure .....	31
6.6	Management of toxicities related to AZD9291.....	32
6.6.1	Pulmonary Symptoms.....	32

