### 1.3 Number of Patients

Overall Survival (OS) is the primary efficacy endpoint for this study. Median OS is assumed to be approximately 21-25 months in patients with advanced or metastatic EGFR T790M mutation-positive NSCLC who have received prior therapy with an EGFR-TKI and are receiving treatment with AZD9291. While the sample size is not known a priori illustrations of the precision with which OS could be calculated from this real world study are given in the table below. These illustrations assume a study length of 58 months with non-uniform accrual over 40 months and that OS is exponentially distributed.

N	21 Months OS		23 Months OS		25 Months OS	
	n events	95% CI median OS*	n events	95% CI median OS*	n events	95% CI median OS*
500	313	18.8-23.5	297	20.5-25.8	283	22.3-28.1
1000	627	19.4-22.7	595	21.2-24.9	566	23.0-27.1
1500	941	19.7-22.4	893	21.5-24.6	800	23.3-26.8
2000	1255	19.9-22.2	1191	21.7-24.3	1133	23.6-26.5
3000	1883	20.1-22.0	1787	22.0-24.1	1700	23.8-26.2
3500	2197	20.1-21.9	2085	22.0-24.0	1983	23.9-26.1

\*95% CI is based on the formula in Collet 1994 (Collett, 1994)

Therefore if 3500 patients enter the study globally and the median OS is 25 months the 95% confidence interval (CI) around this survival figure would be approximately 23.9-26.1 months, assuming 1983 OS events (57% maturity). For Europe, assuming recruitment of 1000 patients and 566 OS events, the equivalent 95% CI would be approximately 23.0-27.1 months.

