## **7 COUNTRY SPECIFIC ANALYSES**

Regional and country level analysis may be performed at the interim analyses and final analysis time points if deemed appropriate.

KM OS analysis and outputs will only be presented for countries that have enrolled a minimum of 150 patients and have at least 60% event maturity to ensure robustness of data for this endpoint.

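### European OS precision is quoted for 1000 patients while the Synopsis plans about 600; one cell of the precision table also carries a wrong event count

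*Protocol*

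**What the plan says.** The Synopsis, under study sites and number of patients, states: "Approximately 600 patients will be enrolled (dosed) in Europe". It places recruitment beyond that number in America and Asia and expects about 3500 patients in all.

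Protocol 9.5 tabulates expected deaths and 95% confidence intervals for median OS at six sample sizes and three medians (21, 23 and 25 months). On its assumptions it says: "These illustrations assume a study length of 58 months with non-uniform accrual over 40 months and that OS is exponentially distributed". The text below the table applies the 3500-patient row to the whole study and the 1000-patient row to Europe: "For Europe, assuming recruitment of 1000 patients the equivalent 95% CI would be approximately 23.0-27.1 months".

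SAP 1.3 reprints the table and words the European statement as: "For Europe, assuming recruitment of 1000 patients and 566 OS events, the equivalent 95% CI would be approximately 23.0-27.1 months".

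The documents are open about the status of these figures. Protocol 9.5 introduces them with "While the sample size is not known a priori illustrations of the precision with which OS could be calculated from this real world study", and the Synopsis says "a total pre-defined recruitment target of treated patients is not applicable for this study".

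**The concern.** The global sentence uses 3500, which agrees with the Synopsis. The European sentence beside it uses 1000, which does not. Both statements are in current operative text, so the conflict does not depend on the version history.

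OS is the primary efficacy endpoint, and this is the only precision that either document gives for Europe by name. SAP section 7 leaves room for a European analysis: "Regional and country level analysis may be performed at the interim analyses and final analysis time points if deemed appropriate". A reader who takes the sentence as the expected European precision will expect a narrower interval than the planned enrolment can give.

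The second point is smaller. Within each column of the table, events should be a constant fraction of N, because the accrual, follow-up and survival assumptions do not change from row to row. One cell in the 25-month column breaks this pattern in both documents.

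**Working it through.** **Inputs.** Event counts and intervals: the table in Protocol 9.5 and SAP 1.3. Planned European N: 600 (Synopsis). European N used for precision: 1000, with 566 deaths (SAP 1.3). Study length 58 months and exponential survival: Protocol 9.5. The shape of the non-uniform accrual is not given, so the event counts cannot be rebuilt from first principles (uniform accrual would give 63.3% events at a median of 25, not the tabulated 56.7%). The check therefore uses the table's own event fractions.

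**Reproducing the printed intervals.** The documents cite a textbook formula without printing it. For an exponential median *m* estimated from *d* deaths, the log-scale interval is

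*m* × exp(±1.96/√*d*).

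- *m* = 25, *d* = 566: 23.02 to 27.15 (printed 23.0-27.1).
- *m* = 25, *d* = 1983: 23.92 to 26.13 (printed 23.9-26.1).

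All 18 printed intervals follow from their printed event counts in this way. The linear form *m* × (1 ± 1.96/√*d*) does not fit: for 283 deaths it gives 22.09 to 27.91, against 22.3-28.1 printed.

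**Europe at 600 patients.** Event fractions come from the 3500 row; deaths are 600 times the fraction.

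| Median | Event fraction | Deaths at N=600 | 95% CI at N=600 | Printed at N=1000 |
|---|---|---|---|---|
| 21 | 2197/3500 = 0.6277 | 377 | 19.0-23.2 | 19.4-22.7 |
| 23 | 2085/3500 = 0.5957 | 357 | 20.7-25.5 | 21.2-24.9 |
| 25 | 1983/3500 = 0.5666 | 340 | 22.5-27.8 | 23.0-27.1 |

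At a median of 25 the width is 27.80 − 22.48 ≈ 5.3 months, against 27.15 − 23.02 ≈ 4.1 at N=1000. The ratio is about 1.29 at each median, as √(1000/600) = 1.29 would suggest.

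**Does the unknown accrual shape matter?** Take the most favourable case, in which every European patient is followed for all 58 months. Deaths at a median of 25 are 600 × (1 − 2^(−58/25)) = 479.8, giving 22.86 to 27.34, width 4.48. That is still wider than the stated interval. Obtaining 566 deaths would need 566/0.5666 = 999 patients at the table's event fraction, or 566/(1 − 2^(−58/25)) = 708 patients with full follow-up. In the other direction, if only 283 of the 600 died (47%), the interval would be that of the printed N=500 row, 22.3-28.1.

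**The cell for N=1500, median 25.**

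| N | Events printed | Events/N |
|---|---|---|
| 500 | 283 | 0.5660 |
| 1000 | 566 | 0.5660 |
| 1500 | 800 | 0.5333 |
| 2000 | 1133 | 0.5665 |
| 3000 | 1700 | 0.5667 |
| 3500 | 1983 | 0.5666 |

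The other two columns are steady at about 0.627 (median 21) and 0.595 (median 23). The 25-month column implies 1500 × 0.5666 = 850 events. The printed interval of 23.3-26.8 matches 800 events (23.33 to 26.79), not 850 (23.37 to 26.74), so the count was carried into the interval.

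**The case against.** The European sentence is conditional. It says what it assumes, sits among figures labelled as illustrations, and is arithmetically right for 1000 patients. The study is descriptive, with no fixed recruitment target, and the N=500 and N=1000 rows bracket 600 for any reader who looks. Nothing operational rests on the figure: regional analyses are optional, region is not a listed subgroup in SAP 4.2.7, and the OS reporting threshold in SAP section 7 (150 patients and 60% maturity) applies by country. The shift of about 0.5 to 0.7 month per limit is small beside the 4-month span of assumed medians. The global event fraction may not suit Europe, where earlier entry could give longer follow-up and more deaths. Re-issuing documents also has a cost: Protocol 11.5 may require contact with ethics committees, and the SAP is already at version 7.0 with an addendum dated 03 November 2020.

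Much of this stands. No decision is affected, the error in the N=1500 cell is cosmetic, and European follow-up could differ from the global pattern in either direction. But the objection does not remove the conflict. A generic N=1000 row is unobjectionable; the fault lies in attaching it to Europe when the same protocol plans 600 there. Longer European follow-up does not rescue the figure either, since the most favourable case still falls short of it.

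**Conclusion.** The inconsistency is real and appears in both documents. At the planned European enrolment, the interval at a 25-month median is about 22.5 to 27.8 months (width 5.3), not 23.0-27.1 (width 4.1). With 58 months of follow-up for everyone it would be no better than 22.9 to 27.3. The 600-patient figures rest on the table's exponential model and on the global event fraction holding in Europe. Country closure after reimbursement (Protocol 10.2.4) could lower the number of deaths; earlier European entry could raise it.

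The N=1500, median-25 cell is wrong by about 50 events, or 0.1 month per limit once rounded.

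Neither point touches a test, a power statement or the 3500-patient precision. The European sentence should be corrected because it overstates the precision of the primary endpoint for a named region; the cell is a minor correction.

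**What to change.** In both Protocol 9.5 and SAP 1.3:

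1. Restate European precision for the planned number, along these lines: *With about 600 European patients and the table's global accrual and follow-up assumptions (about 340 deaths), a median of 25 months would have a 95% CI of roughly 22.5 to 27.8 months; earlier country closure would widen this, and longer European follow-up would narrow it.* If 1000 is the intended European number, change the Synopsis instead. Either way the two must agree.
2. Optionally add an N=600 row: 377 events, 19.0-23.2; 357 events, 20.7-25.5; 340 events, 22.5-27.8.
3. Correct the N=1500, median-25 cell to about 850 events and 23.4-26.7.

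The cost is one sentence and one cell in each document, plus whatever notification Protocol 11.5 and local rules require. The stated European precision becomes less favourable. No additional patients, data or analyses are needed.
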